1. AMENDMENT HISTORY

Amendment No.	Protocol Version No.	Date issued	Author(s) of changes	Details of Changes made
	3	1/11/17	[name] [name] [name]	
SA#02	4	1/04/18	[name] [name]	 Clarifications, Typos, Additional Author. Follow up duration extended to 6 months from 8-16 weeks. Inclusion Criteria (i) amended to say that all patients need to be able to give consent not just the acute patients The number of visits the Healthy Volunteers will have is 2 instead of 3. ACQ questionnaire in the table schedule was supposed to have been the AQLQ questionnaire, however this typo was missed at the last amendment. ACQ amended to AQLQ Added the NASA Task Load index. CRP & FBC blood tests have been removed from the pneumonia V1b visit. Quadriceps Ultrasound removed in Heart failure patients. 4 Meter Gait in Heart failure subjects removed from Visit V1a and added to. This test has been

Page 6 of 46

			completely removed from Healthy
			Volunteers.
		-	Physical exam removed from Visit 2
			in Healthy Volunteers.
		-	Review of AE & SAE at Visit 1a
			removed for Paediatric patients.
		-	Lung function clarification given that
			spirometry is both Pre and Post
			bronchodilator to match the patient
			information sheets.
		-	Removed the questionnaire from
			the appendix of the protocol.

2. SYNOPSIS

Trial Design Pr	onsor Reference 0569 ospective Acute Care 'Real Life' Observational Study
Trial Participants Pa	
со	tients with acute breathlessness in the following (post-acute pathway nfirmed) strata:
1 * *	Acute Heart failure , characterised by a clinician diagnosis, and a proto-typical sponse to treatment.
re	Community acquired pneumonia , defined as new radiological consolidation sponsive to treatment according to the British Thoracic Society (BTS) mmunity acquired pneumonia guidelines.
wi pr) Adult exacerbations of asthma and COPD, defined as a clinician diagnosis th objective confirmatory evidence of disease based upon historical or ospective measurements, requiring an acute change in treatment (e.g. tibiotics, oral corticosteroids or increased bronchodilator therapy)
(iv) Paediatric exacerbations of acute childhood wheeze and or confirmed asthma
he an wi	Age and/or Home environment matched Adult/Sibling/Parent/Spousal althy volunteers, who have no prior history of asthma, COPD, heart failure d have not been admitted to hospital with community acquired pneumonia thin 6 weeks of the baseline study visit. Additional healthy volunteers will also recruited from local databses.
as) Stable state aged matched participants with a confirmed diagnosis of thma, COPD or heart failure, that have not had and exacerbation of their sease within the preceding 6 weeks.
Planned Sample Size Ar	interim analysis was conducted in September 2017 to determine the sample
siz	e of the ember acute study. Guided by literature search, a panel of 10 pre
sp	ecified aldehyde biomarkers derived from GCMS analysis were supplied. The
bio	omarkers were normalised to a common standard and were not background
su	btracted.
A	closed formula from Hsieh et al, Statis med 1998, was utilised to calculate
sa	mple sizes from logistic regression models of the 10 aldehydes with acute
br	eathlessness as the outcome measure. The sample size estimates are also
re	evant to acute class comparisons vs. the sum of other acute classes.
Ва	sed upon the samples size estimates we would have an 80% power at the 5

	% significance level to detect an odds ratio of association of 1.2 for a given
	disease class with minimum of 55 patients per disease class.
	Discovery Phase (years 1-2): Acute Heart failure (n=55-100), Community acquired pneumonia (n=55-100), adult exacerbations of asthma and COPD (n=110-200), paediatric exacerbations of acute childhoodwheeze and/or confirmed asthma (n=50-100), Age/Home environment matched Adult/Sibling/Parent/Spousal healthy volunteers (n=55-150 adults/50 children)
	Replication Phase (years 3-4): Acute Heart failure (n=55-100), Community acquired pneumonia (n=55-100), adult exacerbations of asthma and COPD (n=110-200), paediatric exacerbations of acute childhood wheeze and/or confirmed asthma (n=25-50), Age/Home environment matched Adult/Sibling/Parent/Spousal healthy volunteers (n=55-75 adult/25 children)
	Additional patients with stable COPD/Asthma/Heart failure n=200 Total Sample Size = 550-1250 patients.
Follow-up duration	Acute care participants will have up to 2 visits whilst an inpatient followed by a 'Post-Acute Event Recovery' at a minimum of 6 weeks post discharge and up to 6 months. Stable state participants and healthy volunteers will have 2 visits over 16 weeks. All participants will have outcome data 2 years post recruitment.
Planned Trial Period	3 years
Primary Objective	To evaluate the sensitivity, specificity, positive and negative predictive value of metabolomic biomarkers in exhaled breath samples to identify acute breathlessness, defined as one or more of (i) patient defined acute breathlessness and/or a (ii) 1 unit increase in Extended Medical Research Council breathlessness score (eMRC).
Secondary Objectives	To replicate selected metabolomic breath biomarker panels of acute breathlessness using a combination of both (i) discovery technologies (including GC-MS) and (ii) point of care auto tuned breath sensing devices (including linear IMS, CMS, PTR-MS).
	2) To evaluate the primary endpoint stratified by breathlessness as follows (i) change in eMRC by 1 unit, (ii) patient defined breathlessness and (iii) 100 mm visual analogue score for breathlessness
	To discover and replicate metabolomic breath biomarkers that differentiate (i) Acute Heart failure, (ii) Community acquired pneumonia, (iii) Adult exacerbations of asthma and COPD

	To quantify the level of clinical uncertainty in the primary diagnosis using a 100 mm visual analogue scale and independent clinical adjudication of case notes blinded to the following blood biomarkers (i) CRP (ii) blood eosinophils (iii) BNP (iv) Troponin-I but not clinical history and chest X-ray.
	To identify and discover metabolomic breath biomarkers of acute childhood wheeze and or confimed asthma.
	To clinically validate metabolomic breath biomarkers generated above using a combination of existing pathology markers e.g. BNP, CRP, blood eosinophils and troponin-I and other clinical relevant prognostic scoring tools e.g DECAF, CURB65 and Heart failure risk calculator http://www.heartfailurerisk.org/ ^[19]
Exploratory Objectives	To evaluate the dynamic profile of breath biomarkers during (i) the acute state, (ii) in the recovery state post exacerbation.
	To evaluate the relationship between breath metabolomic biomarkers and health status/ functional measures:
	- Health status measures
	- Physical performance
	3) To evaluate the relationship between metabolomic breath biomarkers and clinical outcomes including (i) hospital readmission at time points up to 2 years (ii) response to standard clinical therapy and (iii) death.
	To explore and develop breath metabolomic biomarkers of multi- morbidity
	 To evaluate the relationship between diet, lifestyle and environment upon breath metabolomic biomarkers.
	6) To generate a biobank of DNA, RNA, urine, plasma, serum and sputum samples for future breathomic and other 'omic molecular pathology studies (including proteomic, transcriptomic, genomic and metabalomic studies).
Investigational Medicinal	None: Patients will follow their standard acute care pathways
Products	

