5.2 Secondary Objectives

- To replicate selected metabolomic breath biomarker panels of acute breathlessness using a combination of both (i) discovery technologies (including GC-MS) and (ii) point of care auto tuned breath sensing devices (including linear IMS, CMS, PTR-MS).
- To evaluate the primary endpoint stratified by breathlessness as follows (i) change in eMRC by 1
 unit, (ii) patient defined breathlessness and (iii) 100 mm visual analogue score for breathlessness
- To discover and replicate metabolomic breath biomarkers that differentiate (i) Acute Heart failure,
 (ii) Community acquired pneumonia, (iii) Adult exacerbations of asthma and COPD
- To quantify the level of clinical uncertainty in the primary diagnosis using a 100 mm visual analogue scale and independent clinical adjudication of case notes blinded to the following blood biomarkers (i) CRP (ii) blood eosinophils (iii) BNP (iv) Troponin-I but not clinical history and chest X-ray.
- To identify and discover metabolomic breath biomarkers of acute childhood wheeze and or confimed asthma.

To clinically validate metabolomic breath biomarkers generated above using a combination of existing pathology markers e.g. BNP, CRP, blood eosinophils and troponin- I and other clinical relevant prognostic scoring tools e.g DECAF, CURB65 and Heart failure risk calculator http://www.heartfailurerisk.org/^[19]

- Replication of acute breathlessness biomarkers will be according to the following predefined primary diagnoses in the replication phase:
 - (i) Acute Heart failure (n=55-100),(ii) Community acquired pneumonia (n=55-100), (iii) adult exacerbations of asthma and COPD (n=110-200),(iv) paediatric exacerbations of acute childhood wheeze and confirmed asthma (n=25-100),(v) age/home environment matched adult/spouse/sibling/parent control subjects (n=55-75 adults/25 children)
 - 5.3 Exploratory End Points (where applicable)
 - 1) To evaluate the dynamic profile of breath biomarkers during (i) the acute state, (ii) in the recovery state post exacerbation.

Page 15 of 46

- 2) To evaluate the relationship between breath metabolomic biomarkers and health status/ functional measures:
- Health status measures
- Physical performance
 - 3) To evaluate the relationship between metabolomic breath biomarkers and clinical outcomes including (i) hospital readmission at time points up to 2 years (ii) response to standard clinical therapy and (iii) death.

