21.2 Closed formula for logistics regression models

82 acutely breathless adults (asthma:35, community acquired pneumonia :16, COPD:26) and 17 healthy controls were utilised for the analysis.

A panel of 10 pre specified aldehyde biomarkers derived from GCMS analysis were supplied. The biomarkers were normalised to a common standard and were not background subtracted.

A closed formula from Hsieh et al, Statis med 1998, was utilised to calculate sample sizes from logistic regression models of the 10 aldehydes with acute breathlessness as the outcome measure. The sample size estimates are also relevant to acute class comparions vs. the sum of other acute classes.

The results of the analyses are outlined in the figure below (each BRI number annotates a specific aldehyde).

Based upon the sample size estimates we would have an 80% power at the 5 % significance level to detect an odds ratio of association of 1.2 for a given disease class with 55 patients per disease class. Given the fact that MRC EMBER seeks to discover and replicate breath VOCs amongst 5 adults classes (CAP, heart failure, COPD, asthma and healthy aged matched subjects).

We would require 110 patients per class – 550 patients across the program to achieve these aims.

Commented [CSB1]: This is not a complete sentence. There is a clause missing, or else the punctuation needs adjustment.

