21.6 Paediatric Recruitment Plan: Acute Study

Acute childhood wheeze and or confirmed asthma.

Revised to 50 Discovery and 25 replication, based upon current recruitment.

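### The synopsis power statement (80% at a minimum of 55 per disease class) is not limited to adults, yet the paediatric class is planned at 50 and 25 and was never part of the sizing calculation.

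*Protocol*

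**What the plan says.** **Synopsis, Planned Sample Size.** The statement is that "we would have an 80% power at the 5" per cent "significance level to detect an odds ratio of association of 1.2 for a given" "disease class with minimum of 55 patients per disease class". Nothing in it restricts the class to adults. The participant list in the same synopsis has paediatric wheeze/asthma as stratum (iv). The phase-by-phase numbers that follow give that class 50-100 in discovery and, in replication, "paediatric exacerbations of acute childhood wheeze and/or confirmed asthma (n=25-50").

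**Appendix C, 21.2.** The closed formula "was utilised to calculate sample sizes from logistic regression models of the 10 aldehydes with acute breathlessness as the outcome measure". The appendix adds: "The sample size estimates are also relevant to acute class comparions vs. the sum of other acute classes". The data were from 82 acutely breathless adults and 17 healthy controls, and the target was five adult classes. Sections 21.4 and 21.5 name the same five classes (healthy, asthma, COPD, pneumonia, heart failure) at 55 per phase.

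**Appendix C, 21.6.** The whole basis for the paediatric number is: "Revised to 50 Discovery and 25 replication, based upon current recruitment".

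**Where children enter the analysis.** Section 10.1 makes childhood wheeze/asthma level (4) of the class outcome. Section 5.2 says "Replication of acute breathlessness biomarkers will be according to the following predefined primary diagnoses in the replication phase" and lists the paediatric class as item (iv). The objective specific to children, also in 5.2, speaks of identifying and discovering markers and does not mention replicating them.

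**The concern.** The synopsis gives one power figure and one minimum class size, then lists a class that does not meet the minimum. In discovery the shortfall is small and arises at the lower limit (50 against 55). In replication the whole synopsis range, 25-50, lies below 55. Someone who reads only the synopsis has no signal that the 80% was never worked out for children, because the restriction appears only in Appendix C.

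What is at stake is how a paediatric replication result is read. If the 80% is taken to cover children, a non-significant result in 25 children looks like evidence against the marker. In fact a set of that size would miss a true marker of the assumed strength about as often as not.

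**Working it through.** **1. Inputs.** Power 80%, level 5%, odds ratio 1.2, 55 per class (synopsis). Four acute adult classes of 55, so 220 acute adults per phase, and 55 healthy adults (21.5). Paediatric class 50 and 25 (21.6), with 50 and 25 healthy children (synopsis). Sidedness is not stated; two-sided is assumed. Then z(0.975) + z(0.80) = 1.960 + 0.842 = 2.802.

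**2. Can the stated 80% at 55 be reproduced?** For a continuous covariate the Hsieh formula is N = (1.960 + 0.842)² / [p(1−p)(ln OR)²], with the odds ratio per standard deviation (SD) and (ln 1.2)² = 0.03324.
- p = 0.5: 7.849 / (0.25 × 0.03324) = 945 in total.
- p = 0.2: 7.849 / (0.16 × 0.03324) = 1,476 in total.
- Power with 55 in the class is Φ(√[n1·n0/(n1+n0)] × ln 1.2 − 1.960). This gives 16% for 55 v 55 and 23% for 55 v 220.

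So it does not reproduce per SD. It would hold if 1.2 is per raw unit and the marker SD is about 2.3 to 2.9 units (odds ratio per SD about 1.5 to 1.7). The text gives neither the unit nor the SD, and the results figure is not shown. The steps below therefore take the 80% at 55 as given and only rescale it.

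**3. Scaling by class size alone** (same effect, same marker spread): power = Φ(2.802 × √(n/55) − 1.960).
- n = 50: 2.802 × 0.9535 = 2.672; Φ(0.712) = 76%.
- n = 25: 2.802 × 0.6742 = 1.889; Φ(−0.071) = 47%.

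A one-sided 5% test would give 77% and 51%.

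**4. Allowing for the comparator.** Replace n/55 by m/m₀, where m = n1·n0/(n1+n0) for the paediatric contrast and m₀ is the same quantity for the contrast assumed to have 80% power.

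| Paediatric contrast | m | Contrast assumed to have 80% | m₀ | Power |
|---|---|---|---|---|
| 25 v 220 acute adults | 22.4 | 55 v 165 | 41.25 | 54% |
| 25 v 220 acute adults | 22.4 | 55 v 220 | 44 | 52% |
| 25 v 25 healthy children | 12.5 | 220 v 55 | 44 | 32% |
| 25 v 25 healthy children | 12.5 | 55 v 55 | 27.5 | 47% |
| 50 v 220 acute adults | 40.7 | 55 v 165 | 41.25 | 80% |
| 50 v 50 healthy children | 25 | 220 v 55 | 44 | 56% |

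The n = 25 results run from about 32% to 54%. They are not limits. Calibrating on 55 v 55 and applying that to 25 v 220 gives 72%, though this assumes the 80% belonged to a contrast that 21.2 does not name. Using the formula directly per SD gives 9% to 14%.

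**5. The paediatric counts side by side.**

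| Section | Discovery | Replication |
|---|---|---|
| Synopsis | 50-100 | 25-50 |
| 5.1 / 5.2 | 50-100 | 25-100 |
| 7.1 | 55-100 | 25-50 |
| 21.6 | 50 | 25 |

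The discovery lower limit is 50 in three places and 55 in 7.1. The replication upper limit is 50 in the synopsis and 7.1, and 100 in 5.2.

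**The case against.** The strongest reply is that no power claim is made for children. The synopsis sentence is conditional on 55 per class, and a class listed below it at 25-50 falls outside the condition. Appendix C is explicit about adults in 21.2, 21.4 and 21.5, and 21.6 is open that the paediatric number follows recruitment. The synopsis minimum total of 550 equals the adult lower limits alone: (55 + 55 + 110 + 55) × 2. Section 10.6 plans to re-size each replication group after discovery, and 10.2 calls the study exploratory.

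Most of this stands. It shows that the calculation was correctly scoped where it was done, and that 21.4 needs no change. It does not repair the synopsis, which drops the scope and counts children among its strata. A later re-sizing does not alter what the synopsis says now.

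Three stronger readings are tempting, and the documents do not support them:
- **That the sponsor miscalculated paediatric power.** No paediatric figure was calculated.
- **That replication power in children is capped at 54%.** That value depends on the comparator, the calibration, n = 25 and a stated 80% that the text does not let one reproduce. At 50 children, simple scaling gives 76%.
- **That children uniquely miss the ±8-point precision in 21.4.** That is a whole-sample figure. A full adult class of 55 also misses it: 1.96 × √(0.16/55) = ±10.6 points.

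Nor does the protocol set any rule that non-significance in children means refutation. That is a risk of interpretation and not a stated plan.

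**Conclusion.** The point holds as a fault of scope in the synopsis, together with inconsistent paediatric counts. The 80% statement and the minimum of 55 apply to adult classes only, and the synopsis does not say so. The paediatric class sits below that minimum at its planned 50 and 25.

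The size is illustrative: about 76% at 50 and 47% at 25 by class-size scaling, with roughly 32-54% at 25 across the contrasts considered. These figures rest on accepting the stated 80% at 55, a two-sided 5% test, and the same effect and marker spread in children as in adults. None of these can be checked from the text. The firm conclusion is the qualitative one: the sizing does not extend to children, and 25 is well short of the class size on which the protocol bases its power.

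**What to change.** 1. In the synopsis, limit the 80% power statement and the minimum of 55 to the five adult classes. State that the paediatric stratum is not sized by that calculation and that its number reflects recruitment.
2. State that paediatric replication results will be reported as estimates with confidence intervals, and that non-significance in that set will not be read as failure to replicate.
3. If a power figure for children is quoted, label it as an illustration, name the comparator and calibration, and do not present it as a design property.
4. Reconcile the paediatric counts across the synopsis, 5.1, 5.2, 7.1 and 21.6: discovery lower limit 50 v 55, and replication upper limit 50 v 100. If 21.6 is the current plan, the other sections should follow it.

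The cost is wording only. No patients are added and no analysis changes; the stated power simply covers fewer classes than the synopsis now implies.

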3. ABBREVIATIONS

AE Adverse event
AR Adverse reaction

BNP B-type natiuretic peptide
BRC Biomedical Research Centre
BRC Biomedical Research Centre
BTS British Thoracic Society
CAU Childrens Assessment Unit
CDU Clinical Decisions Unit
CI Chief Investigator

CMS Compact Mass Spectrometer

COPD Chronic Obstructive Pulmonary Disease

CRF Case Report Form CRP C-Reactive Protein

CTA Clinical Trials Authorisation

DDU Diagnostics Development Unit

DMS Differential Mobility Spectrometry

DSMC Data Safety Monitoring Committee

eMRC Extended Medical Research Council Score

e-CRF Electronic Case Report Form

ECG Electrocardiogram

EC Ethics Committee (see REC)

ECHO Echocardiography

EPSRC Engineering and Physical Sciences Research Council

FEV1 Forced Expiratory Volume in 1 second

FeNO Fraction Exhaled Nitric Oxide

GC-IMS Gas Chromatography Mobility Spectrometry

GC-FAIMS Gas Chromatography Field Asymmetric Mobility Spectrometry

GC-MS Gas Chromatography and Mass Spectroscopy

GCP Good Clinical Practice
GP General Practitioner

GTAC Gene Therapy Advisory Committee

ICF Informed Consent Form

ICH International Conference of Harmonisation

ISF Investigator Site File

IMP Investigational Medicinal Product

LV Left Ventricular

MAARA Midlands Asthma and Allergy Association

Page 11 of 46

MHRA Medicines and Healthcare products Regulatory Agency

MRC Medical Research Council

MRC-EMBER MRC East Midlands Breathomics Molecular Pathway Node

NHS National Health Service

NIHR National Institute for Health Reseach
NRES National Research Ethics Service

PI Principal Investigator

PIL/S Participant/ Patient Information Leaflet/Sheet
PTRMS Proton transfer mass spectroscopy device

PTR-ToF-MS Real time breath monitoring using protocon transfer reaction time of

flight mass spectrometry

R&D NHS Trust R&D Department REC Research Ethics Committee

RV Right Ventricular

SAE Serious Adverse Event

SAR Serious Adverse Reaction

SOP Standard Operating Procedure

SUSAR Suspected Unexpected Serious Adverse Reactions

TMF Trial Master File

UHL University Hospitals of Leicester NHS Trust

VAS Visual Analogue Score
VOCs Volatile Organic Compounds

4. BACKGROUND AND RATIONALE

Patients presenting with acute undifferentiated breathlessness are commonly encountered in admissions units & emergency departments across the United Kingdom. The primary mechanisms that underpin acute breathless are driven by diseases within the cardio respiratory systems. Cardiorespiratory disease accounts for approximately 70 % of acute hospital admissions and therefore is a major health priority in the National Health Service (NHS).

The differential diagnosis of undifferentiated breathlessness includes heart failure, community acquired pneumonia, exacerbations of chronic obstructive pulmonary disease (COPD), and asthma. The diagnosis of these common conditions is based on a combination of clinical history and emergency diagnostics. Importantly, acutely ill patients with multi-morbidity can present and accurate diagnosis remains challenging. It is well recognised that when clinicians remain uncertain of the cause of breathlessness, patients have a longer hospital stay as well as increased morbidity and mortality [1].

Currently, blood biomarkers together with clinical, physiological and imaging parameters are used to stratify patients with acute breathlessness. Common examples of blood pathology markers utilised in routine clinical practice include brain derived natriuretic peptide [BNP] in heart failure ^[2,3], C reactive protein [CRP] and serum procalcitonin in infective bronchitis and pneumonia^[4] and blood eosinophils in a proportion of exacerbations of asthma and COPD ^[5].

These blood biomarkers have clinical utility primarily in patients with single pathologies, but have poor discriminatory power in patients with multi factorial presentations of acute breathlessness. For example the American College of Emergency Physician recommends addition of a single BNP measurement to improve the diagnostic accuracy compared with standard clinical judgment alone in acutely breathless patients. BNP levels of <100 and >500 ng/ml can reliably 'rule out' and 'rule in' acute heart failure respectively [2,3], but there remain a large number of patients with intermediate values between 100-500 where there is often significant diagnostic uncertainty.

It is therefore likely that a variety of clinical, radiological features and biomarkers are required to accurately identify the cause of acute breathlessness. For example the addition of CRP to conventional clinical rule based algorithms modestly improved the positive likelihood ratio of identifying community acquired pneumonia at a low, intermediate or high risk in a large european population study ^[6].

Therefore better biomarkers are required to identify the cause of breathlessness in acutely unwell patients. Ideally these biomarkers would have the following properties (i) they would originate from the target organ of interest, (ii) they would significantly add value to conventional risk scoring and diagnostic algorithms in acute breathlessness e.g. the DECAF score in COPD^[7] exacerbations or the CURB-65 scoring tool in community acquired pneumonia^[8], (iii) they would be minimally invasive and suitable for rapid point of care diagnosis in emergency rooms and on acute admissions units and (iv) they would be have diagnostic value in patients with multi factorial acute breathlessness.

Breath Analysis and Disease

Exhaled breath analysis of volatile chemicals offers the potential to develop more effective biomarkers in acutely breathless patients. The use of breath analysis for disease diagnostics dates back to ancient Greeks where physicians used exhaled breath to diagnose different diseases. Breath odours allow correct associations to certain diseases. For example, the sweet smell of diabetic ketoacidosis, the fishy smell of

Page 13 of 46

breath associated to liver illness, the urine-like odour of kidney disease and the smell of the breath of patients with lung abscesses, caused by the proliferation of anaerobic bacteria [9-12].

More recently, exhaled breath analysis has demonstrated early proof of concept in the diagnosis of acute heart failure [13], ventilator associated pneumonia [14] and stable state airways disease [15]. The validity of breath analysis has also been demonstrated in breathless children [16]. This population is likely to prefer breath-based tests, as these are minimally invasive. Importantly, a variety of point of care sensors are now available to evaluate potential exhaled breath biomarkers in emergency care settings.

The proposed program of research will identify and evaluate the diagnostic and prognostic value of exhaled breath metabolomic biomarkers in acute cardio respiratory breathlessness and common indicator diagnoses associated with acute cardio respiratory breathlessness. Specific indicator conditions have been selected according to their (i) relatively high prevalence, (ii) high unmet need, mortality and morbidity and (iii) need to develop better diagnostic and prognostic algorithms in acute care pathways.

The focus of the research program will be to phenotype using a combination of 'discovery' and near-patient care breath sampling technologies in acutely breathless patients attending two acute admissions units within Leicestershire. The indicator diagnoses of interest are (i) acute heart failure, (ii) exacerbations of adult asthma and COPD, (iii) community acquired pneumonia and (iv) paediatric exacerbations of acute childhood wheeze and confirmed asthma. Other disorders that are associated with acute breathlessness including exacerbations and acute presentations of pulmonary fibrosis, acute pulmonary embolism will not be studied within the program due to low prevalence, lack of standardised definitions and likely small sample size (pulmonary fibrosis) and adequate acute companion diagnostics (pulmonary embolism).

The program will be divided into two phases. **Phase 1**, a discovery phase to identify putative breath biomarker panels and **phase 2**, a validation phase to replicate and validate selected biomarkers within phase 1 using point of care breath sensing devices.

Patient level clinic-pathological and outcome data (spanning the entire acute pathway) will be collected in parallel to breath sampling. In addition, breath samples will be acquired during the recovery from the acute state and in the stable state post exacerbation to better understand the kinetics of breath analytes associated with these diseases.

A parallel cohort of age/home environment matched Adult/ parent/sibling/spousal healthy volunteers will also be recruited and evaluated at selected matching time points with breath analysis and a range of questionnaires to evaluate factors that are known to influence the metabolome including diet, lifestyle and the environment. Additionally patients with stable asthma, COPD and heart failure will be recruited from primary and secondary care as disease control populations.

